
above and some patients are pre-assigned to each component to stabilize the model, i.e. the first component includes those deliveries within 1 week of GA at randomization and the second component includes the patients who deliver after 38 weeks of GA.
 
The model parameters can then be estimated using PROC FMM from SAS 9.4 by maximizing the likelihood. Point estimate, associated 95% confidence intervals and p-values for the overall average difference between Retosiban and Atosiban is then derived using weighted average of model parameter estimates and variance from each sub-population of mixture model.
 
 • Additionally, treatment by GA at randomization interaction and treatment by progesterone use interaction will also be investigated. • Terms fitted in the FMM model will include: 
 
 Fixed Categorical:	TRT, EP and their interaction term (TRT*EP). Interaction will be included only if the interaction is statistically significant (at 0.05 level of significance).	
 
 Fixed Continuous Covariates:	GA and interaction term (TRT*GA). Interaction will be included only if both interaction are statistically significant (at 0.05 level of significance).	
 
 Repeated:	None	
 
 		Fixed Categorical:	TRT, EP and their interaction term (TRT*EP). Interaction will be included only if the interaction is statistically significant (at 0.05 level of significance).	Fixed Continuous Covariates:	GA and interaction term (TRT*GA). Interaction will be included only if both interaction are statistically significant (at 0.05 level of significance).	Repeated:	None
Fixed Categorical:	TRT, EP and their interaction term (TRT*EP). Interaction will be included only if the interaction is statistically significant (at 0.05 level of significance).						
Fixed Continuous Covariates:	GA and interaction term (TRT*GA). Interaction will be included only if both interaction are statistically significant (at 0.05 level of significance).						
Repeated:	None						
SAS Code							
<pre>proc fmm data=xxx TECHNIQUE=xxx. partial=xxx ; class TRT EP; model T2D = TRT EP GA TRT*GA TRT*EP/ k=2; probmodel TRT EP GA TRT*GA TRT*EP; run;</pre>							
Model Checking & Diagnostics							

 • Refer to Appendix 9: Model Checking and Diagnostics for Statistical Analyses. 							
Model Results Presentation							

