
 • Point estimates of the treatment means and standard deviation will be presented, together with the estimate of the treatment mean differences (retosiban – atosiban), the corresponding 95% confidence intervals and p-value. 							
Summary Results Presentation							

 • The following plot of the time to delivery per treatment will be generated. 
 - Kaplan-Meier Plot of Time to Delivery • Observed values using descriptive statistics will be presented for each treatment group. • In addition, time to delivery or retreatment/subsequent preterm labor will be summarized using descriptive statistics. 							

Primary Statistical Analysis
Sensitivity and Support Statistical Analysis

 Time to delivery will be analyzed using an analysis of covariance adjusting for the covariate of GA at randomization and established progesterone use (yes or no). Additionally, interactions between GA at randomization and treatment and established progesterone use and treatment will also be investigated. Observed values using descriptive statistics will be presented within defined subgroups in Section 5.1.

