11.6.2.2. Handling of Missing/Partial Dates

Element	Reporting Detail
---------	------------------

Element	Reporting Detail				
General	Partial dates will be displayed as captured in subject listing displays.				
Concomitant Medication	Partial start dates of prior and concomitant medications will be assumed to be the earliest possible date consistent with the partial date. In the case of a missing year, the year will be assumed to be the year part of informed consent date of that subject. In the case of a completely missing start date, the start date will be assumed to be prior to date of the first administration of study medication. Partial stop dates of prior and concomitant medications will be assumed to be the latest possible date consistent with the partial date. In the case of a completely missing stop date, the medication will be assumed to be ongoing.				
Time to Delivery	
For the delivery date/time of the primary endpoint,
 
 Missing data with respect to time to delivery endpoint is unlikely to occur. If it occurs and the dates are missing, the last assessment date of a mother prior to delivery phase will be used. If the times are missing, a "00:00" will be used for the time. 				
Adverse Events (General)	
 If the dates are missing for on-treatment, or post-treatment AEs, imputation of AE dates may be performed if needed. The eCRF allows for the possibility of partial dates (i.e., only month and year) to be recorded for AE start and end dates; that is, the day of the month may be missing. Start or end dates which are completely missing (i.e. no year specified) will remain missing, with no imputation applied. There will be no imputation for AE data listings 				

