11.7.1. Time to Delivery

The time to delivery is defined as the days between the delivery and start time of the infusion of IP. If the delivery date is missing or unknown i.e. subjects withdrew from the study or lost to follow-up, the time to delivery data will be the missing data, which will be handled in below methods.

This analysis addresses the question “What is the prolongation effect for the mother of an initial decision to prescribe treatment, regardless of what subjects received?” This is also referred to as a *de facto* analysis (Carpenter 2013). The treatment effect on the time to delivery will be estimated on randomized subjects regardless of adherence. The delivery data after treatment discontinuation, treatment switch (i.e. at retreatment), or use of rescue medication will be collected and will be included in the primary analysis. Missing data from subjects who withdraw from study participation will be imputed using last contact date or last record available in the study database. The last record are those clinical records that the subjects were last contacted but remained undelivered. For those subjects who are lost to follow-up, a date of birth of delivery date will be obtained from the search of national database if applicable.

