11.7.2. Neonatal Composite Outcome

Neonatal Composite outcome is proportion of neonates with any diagnosis from the neonatal morbidity and mortality composite determined up to 28 days after EDD (of 40^{0/7} weeks).

This analysis is also a *de facto* analysis as defined for time to delivery, and will include all mother and neonate pairs regardless of adherence. The delivery data after treatment discontinuation, treatment switch (i.e. at retreatment), or use of rescue medication will be collected and will be included in the primary analysis.

Analysis of the primary endpoint will be performed using multiple imputation methods described as below (Carpenter et al 2013). The MI method will be implemented with the SAS® MI procedure, using the logistic regression method. The model includes treatment (TRT) and GA at birth (GA_birth) as predictors, where GA at birth is considered complete with missing values (if any) being imputed with the last contact date or last record available. PROC MI will replace each missing neonatal composite score with a set of plausible values, assuming data are MAR. The missing data will be filled in 1000 times to generate 1000 complete data sets. Sample SAS® code of the procedure can be found in below:

```
proc mi data=dsetin seed=xxx out=dsetmi n impute=1000;
  class TRT composite;
  monotone logistic;
  var TRT GA_birth composite;
run;
```

Once the 1000 completed datasets are produced, analysis of the neonatal composite outcome will be repeated on these imputed datasets, using a logistic regression model to estimate the effect of treatment on the outcome adjusting for GA at randomization(GA_rand) and progesterone use as covariate:

```
proc logistic data=dsetmi;
  class TRT(desc);
  model composite(event='1') = TRT GA_rand EPU;
  ods output PARAMETERESTIMATES=parms ODDSRATIOS=odds;
  by _Imputation_;
run;
```

PROC MIANALYZE will then be used to combine the results of analyses on the multiply imputed datasets based on Rubin's combination rules (Rubin, 1987).

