11.7.4. Length of Hospital Stay

The handling of missing data in neonatal hospital length of stay can be summarized as follows.

Length of hospital stay will be log-transformed (at base 10) and checked for normality prior to analysis. If the normality assumption holds, the missing values in the length of hospital stay will be multiple imputed and then analyzed using an analysis of covariance adjusting for the covariate of GA at entry and established progesterone use (yes or no). If the normality assumption is violated, the missing values will not be imputed and Wilcoxon rank sum test will be performed to compare the two treatments with all observed data.

If the length of stay data is log-normally distributed, the missing data (in log scale) will be imputed using the SAS® MI procedure with the regression method. The model includes treatment (TRT) and GA at birth (GA_birth) as predictors, where GA at birth is considered complete with missing values (if any) being imputed with the last contact date or last record available in the study database. The missing data will be filled in 1000 times to generate 1000 complete data sets. Sample SAS® code of the procedure can be found in below:

```
proc mi data=dsetin seed=xxx out=dsetmi n impute=1000;
  class TRT;
  monotone regression;
  var TRT GA_birth log_length_stay;
run;
```

Once the 1000 completed datasets are produced, analysis of the log-transformed length of hospital stay will be repeated on these imputed datasets, using a regression model to estimate the effect of treatment adjusting for GA at randomization (GA_rand) as continuous covariate and established progesterone use (EPU) as categorical covariate:

```
proc mixed DATA=dsetmi;
  class TRT EPU ;
  model log_length_stay = TRT GA_rand EPU / solution cl;
  lsmeans trtmt / cl diff;
  by _Imputation_;
```

```
ods output diffss=lgdiffs SolutionF=parameters CovB=covb;  
run;
```

PROC MIANALYZE will then be used to combine the results of analyses on the multiply imputed datasets based on Rubin's combination rules (Rubin, 1987):

```
proc mianalyze data=lgdiffs;  
  modeleffects estimate;  
  stderr stderr;  
  ods output PARAMETERESTIMATES=diffs_mi;  
run;
```

The combined results will be back transformed to normal scale afterwards.

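### An unknown delivery date is replaced by the last contact at which the woman was still pregnant, so a right-censored time is analysed as an observed delivery

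*SAP*

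**What the plan says.** The main rule is in SAP 11.7.1: "Missing data from subjects who withdraw from study participation will be imputed using last contact date or last record available in the study database". The next sentence fixes the woman's status on that date: "The last record are those clinical records that the subjects were last contacted but remained undelivered". For women lost to follow-up, "a date of birth of delivery date will be obtained from the search of national database if applicable"; the section does not say what happens if the search finds nothing or does not apply. Protocol 4.4.1.2 counts loss to follow-up as withdrawal, so the last-contact rule then applies to them too. SAP 11.6.2.2 has a parallel general rule. It states "Missing data with respect to time to delivery endpoint is unlikely to occur" and otherwise takes the last maternal assessment before the delivery phase as the date.

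The value goes into the analyses in SAP 7.1.2. The primary model is a two-component normal mixture, and its PROC FMM call has time to delivery as a plain response with no censoring indicator. Some women are fixed in a component in advance: "the first component includes those deliveries within 1 week of GA at randomization". The supporting model is no different in this respect: "Time to delivery will be analyzed using an analysis of covariance adjusting for the covariate of GA at randomization", plus progesterone use. A Kaplan-Meier plot is listed without a censoring rule.

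SAP 11.7.3 uses the same substitution for births before 37 weeks. In SAP 11.7.2, "GA at birth is considered complete with missing values (if any) being imputed with the last contact date or last record available", and it then serves as a predictor when a missing composite is imputed. SAP 11.7.4 does the same for length of stay, unless the log values are not normal: "If the normality assumption is violated, the missing values will not be imputed and Wilcoxon rank sum test will be performed".

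**The concern.** A woman known to be undelivered on a given day has a delivery time longer than that day. Entering the day as her delivery time is an error of known direction, and the plan makes it in the primary endpoint. It has four consequences for her:

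- Her time to delivery is too short.
- If she was last seen within a week, nothing exempts her from pre-assignment to the imminent-delivery component.
- If she was last seen before 37 weeks, she counts as a preterm birth. Women last seen at or after 37 weeks are classed correctly.
- Her gestational age at birth is too low and is treated as known when neonatal outcomes are imputed.

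The rule is not reliably conservative. Similar loss in both arms dilutes the treatment difference, but more loss on atosiban shortens the atosiban times and inflates the retosiban effect. Appendix 7 of the SAP announces sensitivity analyses in its title, yet 11.7.1 contains none for missing dates, and the ANCOVA uses the same substituted values.

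**Working it through.** **Scope.** Only dosed women count: Protocol 4.4.1.1 stops follow-up of undosed women and 8.3.1.2 excludes them from ITT. The affected women are those whose date is still unknown after all recovery attempts.

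**The plan's own figure.** Protocol 4.1 and 8.2.1 randomize 330 to obtain 300 with birth data, assuming 10% missing. This reproduces: 300 × 1.10 = 330 (dividing by 0.90 gives 334). The 10% may include undosed women, so I take 2% to 10% as an assumed range. The 86% power comes from a simulation report outside the documents and cannot be reproduced.

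**One woman.** Randomized at 33 weeks 0 days and last seen undelivered 14 days later: recorded gestational age at birth = (33 × 7 + 14)/7 = 35.0 weeks, a birth before 37 weeks whatever happened next.

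**By formula.** Suppose proportions m_R and m_A are affected, independently of outcome, and last contact falls on average at a fraction f of the true time. With arm means μ_R and μ_A, the shift in the retosiban minus atosiban difference is

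(1 − f)(m_A μ_A − m_R μ_R).

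- Equal m, true difference 9.5 days (Protocol 8.2.1): the recorded difference is 9.5 × [1 − m(1 − f)]. At m = 10% this is 8.79, 9.03 and 9.26 days for f = 0.25, 0.5 and 0.75. At m = 2% it is 9.36 to 9.45.
- Unequal m, f = 0.5, assumed μ_A = 31.16 and μ_R = 31.16 + 9.5 = 40.66: with 15% lost on atosiban and 5% on retosiban, 0.5 × (0.15 × 31.16 − 0.05 × 40.66) = +1.32 days. With the losses reversed, 0.5 × (0.05 × 31.16 − 0.15 × 40.66) = −2.27 days.

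An ANCOVA simulation at 165 per arm under these assumptions gave +1.32 (9.53 to 10.85) and −2.30 (9.51 to 7.21). Across term gestations of 37.5 to 39.5 weeks and no true effect, 15% versus 5% loss gave a bias of about 1.4 to 1.7 days towards the arm with less loss and a type I error of 8% to 9%. Complete cases gave about 5% to 6%. At 48 per arm the bias was about the same size and type I error was 5% to 6%.

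**With weekly contacts.** A second simulation used 400,000 women per arm and the protocol's 1:2:4:8 gestational-age mix. Contacts fell on days 2, 9, 16 and so on, with a constant weekly loss hazard. Nine assumed delivery models were used (true difference 6.9 to 13.2 days; 48% to 58% of controls delivered by day 21). Each affected woman was recorded 28 to 33 days too early. Births before 37 weeks among them went from 13–28% true to 80–85% recorded, and 15–22% were recorded within 7 days.

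| Loss, retosiban / atosiban | Shift in difference (days) |
|---|---|
| 2% / 2% | under 0.1 |
| 10% / 10% | −0.1 to −0.3 |
| 10% / 5% | −1.6 to −1.8 |
| 5% / 10% | +1.3 to +1.5 |
| Equal 3% weekly hazard (14–17% / 11–13% lost) | −1.0 to −1.9 |

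The last row lies outside the 2% to 10% range. It shows that an equal hazard does not mean equal proportions: women who stay pregnant longer have longer to be lost.

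**At the trial's size.** The SAP mixture was fitted without progesterone, because no prevalence is given. It used 49 retosiban and 48 atosiban women and a true difference of 9.9 days; the estimate's standard deviation is about 5 days. One affected retosiban woman moves the estimate by −0.66 day on average (10th to 90th percentile −1.20 to −0.14), and one atosiban woman by +0.55 (0.06 to 1.17). Mean shifts:

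| Loss, retosiban / atosiban | Mixture | ANCOVA |
|---|---|---|
| 10% / 10% | −0.23 | −0.28 |
| 10% / 5% | −1.67 | −1.73 |
| 5% / 10% | +1.19 | +1.22 |

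At equal 10% loss, single trials deviate from their full-data estimate with a standard deviation of 2.3 days. A censored mixture likelihood on the same trials keeps the mean shift within 0.05 day in every scenario, and the deviation at 0.7 to 1.1 days.

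**The case against.** Few cases are likely. Consent asks for a release of maternal and neonatal records (Protocol 4.2), the endpoint comes from records review (6.2.3), the delivery caregiver is identified in advance (3.1.4), calls are weekly (3.1.3), and women who stop treatment stay in follow-up (4.4.2). The 10% was a planning figure for randomized women. Inflation needs more loss on atosiban, and nothing in this double-blind trial suggests that. One case per arm nearly cancels. The trial stopped early, so the estimate is imprecise in any event. The simulated sizes depend on assumptions: at equal 10% loss one simulation gives −0.1 to −0.3 day and the other about −0.5. Loss was simulated as independent of outcome, given arm and time still pregnant, which favours a censored analysis. A custom likelihood may be out of proportion for a handful of women.

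Much of this stands as a limit on size. The number of dosed women is not given, so 97 is an upper bound and the 49/48 split is assumed. The SAP does not say outright that substituted dates count for pre-assignment; that is its natural reading, since nothing separates them from real deliveries. It is also true that 11.7.1 gives no fallback for a failed database search, but 11.6.2.2 covers that woman with another date on which she was still pregnant. None of this makes the substituted date a delivery date. Independent censoring cannot be verified, but it is a weaker assumption than delivery on the day of last contact.

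**Conclusion.** The concern holds. Where a delivery date cannot be recovered, the plan analyses a lower bound as an event in the primary endpoint and carries it into the secondary ones. The direction of error for each affected woman needs no simulation. The effect on the treatment difference is probably small: 0.5 day or less if equal proportions up to 10% are lost, and about 1.2 to 1.8 days either way at 10% versus 5%. With so few women an imbalance of that kind can arise by chance, and the ANCOVA would move with the mixture and not reveal it. These sizes rest on assumed delivery distributions, loss patterns and proportions missing. The rule should be corrected, but if no date is missing it changes no result.

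**What to change.** Before unblinding, when SAP sections 1 and 9 say analysis decisions are settled:

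- Treat women with an unrecovered date as right-censored at their last undelivered contact. Use a censored two-component likelihood, or multiple imputation of delivery time conditional on exceeding that contact, and state the independent-censoring assumption.
- Pre-assign to the imminent component only women with an observed delivery within a week.
- Carry the imputed gestational age at birth into births before 37 weeks, term birth, the composite and, where imputed, length of stay. Combine with Rubin's rules.
- Show these women as censored in the Kaplan-Meier plot.
- Keep last-contact substitution only as a sensitivity analysis.
- Report by arm how many dates the database search recovered and how many stayed unknown.
- Align the missing-date rule in 11.6.2.2 with 11.7.1, and keep its midnight convention for missing clock times.

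The cost is SAP wording and modest programming. The PROC FMM call has no censoring term and the PROC MI calls do not draw truncated delivery times, so new code is needed. No new data are required.

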11.7.2. Neonatal Composite Outcome

Neonatal Composite outcome is proportion of neonates with any diagnosis from the neonatal morbidity and mortality composite determined up to 28 days after EDD (of 40^{0/7} weeks).

This analysis is also a *de facto* analysis as defined for time to delivery, and will include all mother and neonate pairs regardless of adherence. The delivery data after treatment discontinuation, treatment switch (i.e. at retreatment), or use of rescue medication will be collected and will be included in the primary analysis.

Analysis of the primary endpoint will be performed using multiple imputation methods described as below (Carpenter et al 2013). The MI method will be implemented with the SAS® MI procedure, using the logistic regression method. The model includes treatment (TRT) and GA at birth (GA_birth) as predictors, where GA at birth is considered complete with missing values (if any) being imputed with the last contact date or last record available. PROC MI will replace each missing neonatal composite score with a set of plausible values, assuming data are MAR. The missing data will be filled in 1000 times to generate 1000 complete data sets. Sample SAS® code of the procedure can be found in below:

```
proc mi data=dsetin seed=xxx out=dsetmi n impute=1000;
  class TRT composite;
  monotone logistic;
  var TRT GA_birth composite;
run;
```

Once the 1000 completed datasets are produced, analysis of the neonatal composite outcome will be repeated on these imputed datasets, using a logistic regression model to estimate the effect of treatment on the outcome adjusting for GA at randomization(GA_rand) and progesterone use as covariate:

```
proc logistic data=dsetmi;
  class TRT(desc);
  model composite(event='1') = TRT GA_rand EPU;
  ods output PARAMETERESTIMATES=parms ODDSRATIOS=odds;
  by _Imputation_;
run;
```

PROC MIANALYZE will then be used to combine the results of analyses on the multiply imputed datasets based on Rubin's combination rules (Rubin, 1987).

As the estimates of odds ratios follow a log-normal distribution, a log transformation can be applied to normalize these estimates in order to be able to apply Rubin's rules. These combination rules take as input estimates of a statistic obtained from multiple imputed datasets as well as standard errors of these estimates, and produce the overall pooled estimate, overall standard error, confidence interval and a p-value from a univariate hypothesis test of the statistic being equal to zero. An example of SAS® code is given below:

*** log-transform odds ratio estimates and obtain standard error from CIs;

```
data lgodds;
  set odds(where=(index(effect,"TRT")));
  log_or=log(OddsRatioEst);
  log_or_se=(log(UpperCL)-log(LowerCL))/(2*1.96);
run;
```

*** combine transformed estimates;

```
proc mianalyze data=lgodds;
  modeleffects log_or;
  stderr log_or_se;
  ods output PARAMETERESTIMATES=lgsodds_mi;
run;
```

*** back-transform combined values;

```
data odds_mi;
  set lgsodds_mi;
  OddsRatioEst = exp(estimate); * pooled odds ratio;
  LowerCL=OddsRatioEst*exp(-1.96*stderr); * pooled lower limit;
  UpperCL=OddsRatioEst*exp( 1.96*stderr); * pooled upper limit;
run;
```

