2.3. Study Design

Overview of Key Study Design Features	
Design Features:	
 Phase III, randomized, double-blind, double-dummy, multicenter design Subjects are females, aged 18 to 45 years (Sweden) or aged 12 to 45 years (all other countries including UK, Germany, Italy, Israel, South Korea, Belgium, Mexico, Spain and Brazil), with an uncomplicated, singleton pregnancy and intact membranes in preterm labor between 24^{0/7} and 33^{6/7} weeks of gestation.
Dosing:	
 Retosiban treatment will be administered as a 6-mg IV loading dose over 5 minutes, followed by a 6-mg/hour continuous infusion over 48 hours. Atosiban will be given intravenously in 3 successive stages: an initial bolus dose of 6.75 mg using atosiban 6.75 mg/0.9 mL solution for injection, immediately followed by a continuous high dose infusion at 18 mg/hour for 3 hours, then a lower 6 mg/hour infusion for the remainder of the 48-hour treatment period using the atosiban 37.5 mg/5 mL concentrate for solution.
Treatment Assignment:	
 A total of 97 patients were blindly randomly assigned to retosiban or atosiban in a 1:1 ratio. Subjects were stratified by established progesterone treatment (Yes/No) and gestational age at randomization (24^{0/7} to 25^{6/7}, 26^{0/7} to 27^{6/7}, 28^{0/7} to 30^{6/7} and 31^{0/7} to 33^{6/7}). Subjects within each stratum will be randomly assigned in 1:1 ratio to receive either retosiban or atosiban using an IVRS in accordance with the randomization schedule.
Interim Analysis	
 The study was terminated before interim analysis due to feasibility. Details of the interim analysis were written in the IDMC RAP.

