	
 • For the endpoints of neonatal composite outcome, proportion of births prior to $37^{0/7}$ weeks' gestation, and proportion of births at term ($37^{0/7}$ to $41^{6/7}$ weeks' gestation), a logistic regression model will be used for comparing retosiban with atosiban, with GA at randomization and established progesterone use (yes or no) as covariates. The model will use a logit link function to estimate the log odds of percentage of preterm birth. The model will include terms for treatment group, established progesterone use, and GA at randomization. Additionally, interactions between GA at randomization and treatment and established progesterone use and treatment will also be investigated. • Length of hospital stay will be log-transformed (at base 10) prior to analysis. Log-transformed length of hospital stay will be analyzed using an analysis of covariance adjusting for the covariate of GA at randomization and established progesterone use (yes or no). Additionally, interactions between GA at randomization and treatment and established progesterone use and treatment will also be investigated. Wilcoxon rank sum test will also be performed to compare the two treatments if length of hospital stay is not log normal. • Terms fitted in the model will include: Fixed Categorical: TRT, EP and their interaction term (TRT*EP). Interaction will

Key Secondary Efficacy Statistical Analysis	
Fixed Continuous Covariates:	be included only if the interaction is statistically significant (at 0.1 level of significance). GA and interaction term (TRT*GA). Interaction will be included only if the interaction is statistically significant (at 0.1 level of significance).
Repeated:	None
SAS Code	

 Analysis of Covariance: <pre>ods output lsmeans=means diff=diffs tests3=tests; proc mixed data=xxx; class EP TRT; model log_LoS= TRT EP GA TRT*EP TRT*GA/ddfm=kr s; lsmeans TRT /pdiff cl alpha=0.05; run;</pre> Wilcoxon rand sum test: <pre>proc npar1way data=xxx Wilcoxon; class TRT; var log_LoS; ods output wilcoxontest=wtest; run;</pre> 	
Model Checking & Diagnostics	

 Refer to Appendix 9: Model Checking and Diagnostics for Statistical Analyses. 	
Model Results Presentation	

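### The imputation models for the neonatal composite and, if log-normal, length of stay omit GA at randomization and progesterone use, so any effect of these factors beyond GA at birth is diluted in imputed records

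*SAP*

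**What the plan says.** For the neonatal composite, SAP 11.7.2 describes the imputation model in prose ("The model includes treatment (TRT) and GA at birth (GA_birth) as predictors") and repeats it in code ("var TRT GA_birth composite"). The completed data sets are then analysed with a larger covariate set: "model composite(event='1') = TRT GA_rand EPU".

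For log length of stay, SAP 11.7.4 has the same pair: imputation with "var TRT GA_birth log_length_stay", analysis with "model log_length_stay = TRT GA_rand EPU / solution cl". This applies only if stay is log-normal. Otherwise "the missing values will not be imputed and Wilcoxon rank sum test will be performed" on the observed data.

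The two variables left out are the stratification factors of SAP 2.3 ("Subjects were stratified by established progesterone treatment (Yes/No) and gestational age at randomization"). For both endpoints SAP 8.1.2 adds that "interactions between GA at randomization and treatment and established progesterone use and treatment will also be investigated", and keeps an interaction in the model if it is significant at the 0.1 level. SAP 11.11.3 lists the composite by GA group and by progesterone group (Tables 2.151 and 2.152), and stay likewise (Tables 2.321 and 2.322).

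**The concern.** An imputation model should contain at least the variables of the analysis it feeds. If a covariate is left out, missing outcomes are drawn as though it had no effect once the included predictors are known. Pooling those draws with the observed data pulls that covariate's residual effect toward zero, and does the same to any interaction it has with treatment.

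Multiple imputation is the planned main handling of the composite, not a side analysis. SAP 11.7.2 assumes that data are missing at random. With this model that must hold given treatment and GA at birth alone, which is harder to defend if loss to follow-up depends on GA at entry. Both omitted variables are available: SAP 11.6.2.1 gives a fallback for missing GA at randomization and a derivation rule for progesterone use.

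**Working it through.** The plan gives no figure that depends on this choice, so there is none to reproduce.

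**1. Variables side by side**

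| Endpoint | Imputation model | Analysis model | In analysis only |
|---|---|---|---|
| Composite (11.7.2) | treatment, GA at birth | treatment, GA at randomization, progesterone | GA at randomization, progesterone |
| Log stay (11.7.4, if log-normal) | treatment, GA at birth | treatment, GA at randomization, progesterone | GA at randomization, progesterone |

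**2. What still gets through.** SAP 11.5.4 gives GA at birth = (GA at randomization × 7 + time to delivery)/7. GA at birth therefore carries GA at randomization, and it carries progesterone to the extent that progesterone alters delivery time. Only effects beyond GA at birth are lost.

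**3. Size for the composite, by simulation.** Inputs from protocol 8.2.1: stratum mix 7/13/27/53%, 55% of atosiban women delivering within 3 weeks, 10% missing (5% and 20% also run). Assumptions: 20% progesterone use, the retosiban effect, the outcome coefficients, and missingness completely at random. Each setting has 400,000 mothers and one imputation draw per missing share, so small third-decimal differences are noise. The analysis is logistic on treatment, GA at randomization and progesterone.

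| Assumed effect beyond GA at birth | Coefficient | Full data | 5% | 10% | 20% missing |
|---|---|---|---|---|---|
| A: none | GA at randomization | −0.262 | −0.262 | −0.263 | −0.261 |
| | progesterone | 0.011 | 0.009 | 0.013 | 0.002 |
| | treatment | −0.353 | −0.353 | −0.350 | −0.352 |
| B: GA −0.15/week, progesterone log OR 0.7 | GA at randomization | −0.314 | −0.311 | −0.308 | −0.302 |
| | progesterone | 0.469 | 0.444 | 0.420 | 0.375 |
| | treatment | −0.376 | −0.375 | −0.374 | −0.380 |
| C: GA −0.3/week, progesterone log OR 1.0 | GA at randomization | −0.381 | −0.373 | −0.366 | −0.351 |
| | progesterone | 0.649 | 0.615 | 0.583 | 0.523 |
| | treatment | −0.383 | −0.381 | −0.372 | −0.369 |

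**4. Why the dilution follows the missing share.** With missing share f, the completed-data coefficient is roughly (1 − f) × full-data value + f × value among imputed records. In B the values among imputed records are −0.010 for progesterone (truth among those records 0.467) and −0.256 for GA at randomization (truth −0.315). At f = 0.10:

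- Progesterone: 0.9 × 0.469 + 0.1 × (−0.010) = 0.421 (simulated 0.420), a fall of (0.469 − 0.420)/0.469 = 10%.
- GA at randomization: 0.9 × (−0.314) + 0.1 × (−0.256) = −0.308 (simulated −0.308), a fall of 0.006/0.314 = 2%. Most of this coefficient runs through GA at birth and is kept.

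The largest treatment shift is in C at 20% missing: (0.383 − 0.369)/0.383 = 4%.

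**5. With both variables added.** In B, among imputed records, GA at randomization returns to −0.315 and progesterone to 0.449.

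**6. Smaller trials, loss depending on GA at randomization.** With n = 97 and 300 and an assumed residual GA effect of 0.2 log-odds per week, the GA coefficient moves from −0.267 to −0.253 with 14% missing (5%) and to −0.241 with 25% missing (10%). It returns to −0.269 and −0.270 when both variables are included. The treatment log odds ratio moves by 2% or less, for example −0.540 against −0.551 at n = 97.

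**7. Interactions.** Assumed interactions, protocol stratum mix, 10% missing completely at random, 400,000 mothers:

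| Interaction | Full data | SAP model | Main effects added | Interaction terms added as well |
|---|---|---|---|---|
| treatment × progesterone | −0.588 | −0.524 | −0.524 | −0.573 |
| treatment × GA | −0.085 | −0.074 | −0.073 | −0.084 |

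The treatment × progesterone term loses (0.588 − 0.524)/0.588 = 11%, and adding main effects does not recover it. A further run with another assumed treatment × progesterone interaction agrees: −0.401 in full data, −0.367 with main effects added, −0.408 with interaction terms.

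Length of stay was not simulated. The direction follows from the same structure; the size is not computed.

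**The case against.** The strongest reply is that the planned results barely feel this. The pooling code in SAP 11.7.2 keeps only the treatment odds ratio, and 11.7.4 pools only the treatment difference. The diluted covariate coefficients are not themselves reported, and the treatment estimate hardly moves. That stands, and it is why the point is minor.

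A lean imputation model can also be defended with 97 women, especially if few used progesterone. That is fair, but it is a reason for care in fitting rather than for leaving out variables that the analysis model itself includes.

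Two stronger readings are tempting, and the documents do not support either.

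- A reader might infer that imputed values bear no relation at all to the randomisation factors. They do, because GA at birth contains GA at randomization. In setting A the correlation of the composite with GA at randomization among missing cases is −0.280 imputed against −0.281 true. In B it is weakened (−0.282 against −0.339), not absent.
- A reader might infer that the subgroup tables are distorted. The SAP does not say that they use imputed data. The stay tables are titled as summary statistics, and SAP 8.1.2 describes the descriptive statistics for stay as observed values. If the tables use observed data, imputation cannot touch them.

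Nor does the SAP say whether the interactions are examined in the imputed data; the sample analysis code in 11.7.2 and 11.7.4 has none.

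**Conclusion.** The point holds in a limited form. Both imputation models are poorer than the analysis models they feed, in prose and in code. Given treatment and GA at birth, imputed outcomes carry no additional relation to GA at randomization or progesterone use.

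Residual effects of these factors, and their interactions with treatment if tested in imputed data, are diluted by roughly the missing share: about 10% at the protocol's planned 10% missing. The overall treatment effect changes little (at most about 4% in the strongest assumed setting), and nothing changes if there is no residual effect. For stay the point applies only when log-normality holds.

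The existence and size of residual effects are assumptions, since the documents give none. This is a worthwhile tidy-up, not a threat to the main comparison.

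**What to change.** - Add GA at randomization and progesterone use to both PROC MI VAR statements, for example `var TRT EPU GA_rand GA_birth` followed by the outcome, and add EPU to CLASS. Amend the prose in 11.7.2 and 11.7.4 to match.
- Where treatment-by-GA or treatment-by-progesterone interactions are examined in imputed data, put those terms in the imputation model, or impute separately by arm if numbers allow.
- Run Tables 2.151, 2.152, 2.321 and 2.322 on observed data or on data imputed with the fuller model, and say which.

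No new data are needed, and SAP section 1 places final-analysis decisions before database freeze. The downside is two or more extra terms in a sample of 97 women; if progesterone use is rare, the logistic imputation may need the augmented-likelihood option. The change does not address GA at birth being filled from the last contact or record when delivery is unknown, which is a separate matter.
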